## 10 STATISTICAL ANALYSIS

### 10.1 General Considerations

For the Treatment Cohort, all individual subject data will be presented in data listings based on the 116 All Subjects Set.

For the Observational Cohort, listings will be provided only for disposition, demographics, and serious adverse events (SAEs). Listings will be provided based on all subjects enrolled in the Observational Cohort.

#### Treatment Cohort

**Continuous variables** will be summarized using descriptive summary statistics: number of subjects, mean, standard deviation (SD), standard error (SE), median, minimum value (Min), and maximum value (Max). Precisions of the summary for continuous variables are detailed in [Appendix B](#).

**Categorical variables** will be summarized using counts and percentages. Percentages will be presented to 1 decimal place.

**Baseline:** The baseline value is defined as the most recent non-missing measurement (scheduled or unscheduled) before intake of the first dose of study drug in Study 115B, except specified otherwise.

- For ECGs, the baseline will be defined as the average of the pretreatment measurements on the start of Study 115B.
- For LCI-related parameters, the values at each visit will be calculated from the technically acceptable replicates. The baseline of LCI will be the most recent non-

missing value calculated from the technically acceptable replicates before the initial administration of study drug in the Study 115B.

- For sweat chloride, the values at each visit will be based on the averaged measurements from left and right arms. The baseline is defined as the average of the values at screening and the pretreatment measurement on Day 1 of Study 115B. For assessments where there is only 1 pre-first dose sweat chloride measurement available, that measurement will be considered the baseline.

**Change (Absolute Change) from baseline** will be calculated as

$$\text{Post-baseline value} - \text{Baseline value.}$$

**Relative change from baseline** will be calculated and presented in percentage as

$$100 \times (\text{Post-baseline value} - \text{Baseline value}) / \text{Baseline value.}$$

**Unscheduled visits:** Unscheduled visit measurements will be included in the analysis as follows:

- In scheduled visit windows per specified visit windowing rules.
- In the derivation of baseline measurements.
- In individual subject data listings as appropriate.

**Visit windowing rules:** [Appendix C](#) defines the visit window mapping rules to derive the analysis visits for study 116.

Repeated observations within the same visits window:

- For all PD parameters, if there are multiple measurements within a visit window, the record at the scheduled visit will be used. If there are no measurements at the scheduled visit, then 1) the record closest to the target day will be used; or 2) if there are multiple records with the same distance to the target day, the latest record will be used.
- For all safety parameters, if there are multiple measurements within a visit window, then 1) the record closest to the target day will be used; or 2) if there are multiple records with the same distance to the target day, the latest record will be used.

BMI, weight, and stature will follow visit window rules for PD parameters when being considered as PD endpoints; they will follow visit window rules for safety parameters when being considered as safety endpoints. Their corresponding z-scores will be assigned to analysis visits same as BMI, weight, and stature, respectively. Spirometry will follow the PD parameter window rule.

**Incomplete/missing data** will not be imputed, unless specified otherwise.

**Outliers:** No formal statistical analyses will be performed to detect or remedy the presence of statistical outliers, unless specified otherwise.

**Multiplicity:** No multiplicity adjustment will be performed and there is no hypothesis testing.

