#### **Elevation of Liver Function Test Parameters** 11.6.3

#### Mandatory Liver Function Testing

Liver function testing (alanine aminotransferase [ALT], aspartate aminotransferase [AST], gamma-glutamyl transferase [GGT], alkaline phosphatase [ALP], and total bilirubin) must be performed while subjects are receiving LUM/IVA treatment (see Table 3-1 and Section 11.6.2). These blood samples should be processed and shipped immediately per the Laboratory Manual.

Subjects with new ALT or AST elevations of  $\ge 3 \times \text{upper limit of normal (ULN)}$  and clinical symptoms will be followed closely, including repeat confirmatory testing performed by the central laboratory within 48 to 72 hours of the initial finding and subsequent close monitoring of ALT and AST levels, as clinically indicated. If a subject cannot return to the site for liver function testing, a local laboratory may be used. Elevations in LFTs (ALT or AST  $\geq 3 \times ULN$ ) at the local laboratory must be reported immediately to the medical monitor AND the subject must

have the tests repeated and sent to the central laboratory as soon as possible (ideally within 48 to 72 hours).

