### 11.6.5 Electrocardiograms

Standard 12-lead ECGs will be performed using a machine with printout. Standard 12-lead ECGs will be performed with central over-reading. All sites will be provided with ECG machine(s) and associated materials by the central ECG diagnostic service.

Additional standard 12-lead ECGs will be performed at any other time if clinically indicated. The performance of all ECGs will adhere to the following guidelines:

- The subject will be instructed to rest in the supine position for at least 5 minutes, if possible, before having an ECG performed.
- The ECG will be performed before any other procedures that may affect heart rate, such as blood draws.

A printout of the ECG traces will be made for safety review by the investigator and maintained with source documentation. Clinically significant ECG abnormalities occurring during the study through the end of study participation will be recorded as AEs.

A hard copy of the ECG will be printed and signed by the investigator at the site. To ensure the safety of the subjects, the investigator or designee at the investigator site will make comparisons to the predose measurement at Day 1 (baseline). If the QTcF is increased by >45 msec from the shortest baseline QTcF or the absolute QTcF value is >500 msec for any scheduled ECG, 2 additional ECGs will be performed approximately 2 to 4 minutes apart to confirm the original measurement. If either of the QTcF values from these repeated ECGs remains above the threshold value (>45 msec from baseline or >500 msec), a single ECG must be repeated at least hourly until QTcF values from 2 successive ECGs fall below the threshold value that triggered the repeat measurement.

If the QTc value remains above the threshold value (>45 msec from baseline or >500 msec) on repeated measurement or is noted on 2 or more occasions with no identified alternative etiology for the increased QTc, then discontinuation from LUM/IVA treatment may be required after discussion with the Vertex medical monitor or designee. Subjects who have treatment discontinued for increased QTcF should have their QTcF monitored closely until it normalizes or returns to baseline.

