#### **10.5.3 Electrocardiogram**

For the ECG measurements, a summary of raw values and change from parent study baseline will be provided at each scheduled time point of the Current Study Period (including all measurements from Study 116) based on the 116 Safety Set for the overall group, for the following standard digital ECG measurements: RR, PR, QT, and QT corrected for HR (QTc) intervals (Fridericia's correction [ $QTcF = QT/RR^{1/3}$ ], QRS duration, and HR. In addition, the mean value at each time point will be plotted for QTcF.

The number and percentage of subjects meeting the defined threshold criteria during the Treatment-emergent Period of the Current Study Period will be summarized based on 116 Safety Set. The threshold criteria are provided in [Appendix F](#).

The number and percentage of subjects with shift changes from parent study baseline (normal/missing, not clinically significant, and potentially clinically significant according to overall ECG evaluation) to the worst ECG evaluation during the Treatment-emergent Period of the Current Study Period will be summarized based on 116 Safety Set.

Listings will be provided for the ECG measurements.

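### The safety repeat-record rule lets the last same-day repeat ECG replace the scheduled tracing that triggered it, lowering by-visit QTcF summaries

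*SAP*

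**What the plan says.** SAP 10.1 (General Considerations) gives two rules for several records in one visit window. For PD parameters the scheduled-visit record comes first; distance to target and then recency matter only if there is none. Spirometry, a safety endpoint, is assigned to this rule. For the remaining safety parameters the first step is missing: "For all safety parameters, if there are multiple measurements within a visit window, then 1) the record closest to the target day will be used". Ties are settled by recency: "if there are multiple records with the same distance to the target day, the latest record will be used". The same section sends unscheduled measurements to three places, the first being: "In scheduled visit windows per specified visit windowing rules".

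Protocol 11.6.5 sets the ECG trigger: "If the QTcF is increased by >45 msec from the shortest baseline QTcF or the absolute QTcF value is >500 msec for any scheduled ECG". Two further ECGs then follow a few minutes apart. If either is still above the threshold, "a single ECG must be repeated at least hourly until QTcF values from 2 successive ECGs fall below the threshold value".

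SAP 10.5.3 summarises raw ECG values and changes at each scheduled time point and adds: "In addition, the mean value at each time point will be plotted for QTcF". It also counts subjects meeting the Appendix F criteria, and tabulates shifts to the worst ECG evaluation, over the treatment-emergent period of Study 116.

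For liver tests, protocol 11.6.3 asks for "repeat confirmatory testing performed by the central laboratory within 48 to 72 hours of the initial finding". This applies to new ALT or AST elevations of at least 3 × ULN with clinical symptoms. A local-laboratory elevation of that size must also be repeated centrally, ideally on the same timescale.

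**The concern.** A repeat ECG under protocol 11.6.5 exists only because the scheduled one was high, and the series normally stops once values are below the trigger. A rule that keeps the last record therefore chooses according to the result, and always in the same direction. A child whose scheduled QTcF is not high has one tracing, and that one is used. A child whose scheduled QTcF is high has several, and a later one is used.

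ECGs are part of the primary safety endpoint. With about 50 children expected, a QTcF signal may rest on one or two of them, and the by-visit maximum and plot are natural places to look for it.

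**Working it through.** No figure in the plan is at issue, so the check applies the SAP rule to sequences that the protocol can generate. The QTcF values are assumed for illustration.

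**1. Same-day series.** Distance to target is in study days (SAP Appendix C), so all tracings from one day tie and the latest is taken. Changes from baseline in ms at Week 48, target day 337:

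- Both quick repeats below the trigger: +50, +42, +40. Selected: +40.
- Hourly repeats needed: +55, +52, +48, +44, +43. Selected: +43.

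In both, the scheduled value above +45 is replaced by one below it.

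**2. Sequences where this fails.**

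- Visit on the target day, repeats running past midnight: the later-day records are further from target, and the last record of day 337, +49, is selected.
- Visit on day 332, repeats past midnight: the later day is nearer the target, and +43 is selected.
- Series not completed and still above the trigger: the last record, +55, is selected.

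**3. Effect on a by-visit mean.** Shift = (reduction in one child's value) / (children at the visit). With the 50 children expected (SAP 7.2):

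- 10 / 50 = 0.2 ms
- 30 / 50 = 0.6 ms

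With 40 to 56 children, a 10 ms reduction gives 10 / 40 = 0.25 to 10 / 56 = 0.18 ms. The by-visit maximum is not diluted: if the affected child holds it, it can fall by up to the full reduction.

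**4. Effect for one child.** The repeat rule was simulated with one fixed baseline, one reader, independent tracings and an assumed single-tracing SD of 10 or 15 ms. The average is over all visits, triggered or not.

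- True change +45 ms: selected value averages 37.0 (SD 10) or 33.0 (SD 15), so 8 to 12 ms too low.
- True change +30 ms: 28.5 or 25.7, so 1.5 to 4.3 ms too low.

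Using the scheduled tracing at every visit would average the true value under the same model.

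**5. Treatment-emergent tables.** The period maximum in the sequences above stays at +50 to +60. The triggering ECG is a scheduled record inside the treatment-emergent period, and nothing in SAP 10.5.3 restricts the threshold or worst-shift tables to the by-visit record.

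**6. Liver retests.** Let the visit fall d days from target and the retest come L days later. The retest is selected if |d + L| ≤ |d|. With d assumed uniform over the visit window:

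- ±7 days: L = 2 gives 7/15 (47%); L = 3 gives 6/15 (40%).
- Day 15, ±3 days: L = 2 gives 3/7 (43%); L = 3 gives 2/7 (29%).

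These are chances of replacement given that a retest takes place. They are not a bias, because a retest may be higher or lower.

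**The case against.** A reader might infer that every triggered prolongation disappears from the results. The documents do not support that.

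- Step 2 shows that repeats past midnight and unfinished series can leave a value above the trigger. Protocol 11.6.5 itself foresees persistent elevation.
- The trigger is judged at the site against the Day 1 predose value and the shortest baseline QTcF. The analysis uses central readings (protocol 11.6.5) and the average of the Study 115B pretreatment ECGs (SAP 10.1). A repeat below the site's trigger can still exceed +45 ms as analysed.
- Below the trigger does not mean unremarkable. +44 ms lies in the 30 to 60 ms band of SAP Appendix F. A series triggered at above 500 ms could end at 490 ms, over both absolute limits for prolongation (450 ms male, 470 ms female).
- ECG measurements are listed, and clinically significant abnormalities become AEs.

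A second inference is that the threshold and worst-value tables lose these values too. SAP 10.1 names only windows, baseline and listings as uses of unscheduled values, so a higher unscheduled repeat could be handled in two ways. That is a gap in wording, not a demonstrated loss.

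A third is that liver results are pulled towards normal. The retest provision is narrow and has no repeat-until-normal step. A by-visit count above ULN would change only if a value of at least 3 × ULN fell to ULN or below within two or three days, and nothing shows that.

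Finally, the repeats are ordered to confirm the first reading, and a first reading selected for being high overstates the truth: with a true change of +30 ms and SD 10, a triggering reading averages about +49 ms. This is a fair point about a single triggered visit. It does not justify choosing the record by its result when by-visit distributions are being summarised.

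**Conclusion.** The point holds for completed same-day ECG series. There the SAP rule replaces the scheduled QTcF with the last repeat, usually below the site's trigger, in the by-visit summaries, maxima and plot. The selection is one-sided and downward. It moves a 50-child mean by about 0.2 to 0.6 ms per affected child, if the replaced value is 10 to 30 ms lower (assumed), and it can move the by-visit maximum by the full difference. The individual-level figures rest on the assumed SD of 10 to 15 ms and a single reader and baseline.

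The effect is confined to by-visit descriptive outputs in a study without hypothesis testing. For laboratory values, only the possibility of replacement is established. Severity is minor to moderate: worth correcting before database lock, but not a defect that undermines the safety analysis.

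**What to change.** In SAP 10.1, give ECG, laboratory and the other safety parameters the scheduled-record-first rule already used for PD parameters and spirometry, with closest-then-latest kept for windows that have no scheduled record. For a same-day ECG series, name the scheduled tracing as the by-visit record and keep the repeats in the listings.

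As a clarification, add a sentence that the threshold, worst-ECG and lowest oxygen saturation tables use all scheduled and unscheduled records in the treatment-emergent period.

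The cost is SAP wording and a small programming change before lock, with no new data. The price is that at a triggered visit the by-visit value is the unconfirmed first reading; a table footnote pointing to the repeat listing would make that plain.

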## **10.2 Background Characteristics**

### **Treatment Cohort**

#### **10.2.1 Subject Disposition**

The number of subjects in the following categories will be summarized:

- 116 All Subjects Set
- Full Analysis Set
- 116 Full Analysis Set
- 116 Safety Set
- 116 LCI Substudy Set

The number and percentages of subjects will be provided with the number in the 116 Safety Set as denominator. The number of subjects enrolled but never dosed in Study 116 will be provided without a percentage.

- Enrolled but never dosed (only showing number of subjects)
- Completed treatment
- Prematurely discontinued treatment and the reasons for discontinuations
- Last scheduled on-treatment visit completed for subjects who discontinued treatment
- Completed study (any subject who has completed the Safety Follow-up Visit)
- Prematurely discontinued the study and the reasons for discontinuations

Subjects prematurely discontinue treatment before Week 96 due to commercial drug available will be captured in the CRF pages, with primary reason for dosing ended under the “Other” category of “Discontinued” and free text to describe treatment discontinuation due to commercial drug available.

A listing will be provided for subjects who discontinued treatment or who discontinued study with reasons for discontinuation.

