### 5 INTRODUCTION

### 5.1 Background

Cystic fibrosis (CF) is an autosomal recessive disease with serious, chronically debilitating morbidities and high premature mortality and at present, there is no cure. CF affects approximately 70,000 individuals worldwide, with approximately 30,000 individuals in the US. Despite progress in the treatment of CF with antibiotics and mucolytics, the predicted median age of survival for a person with CF is approximately 40 years. Although the disease affects multiple organs, progressive loss of lung function is the leading cause of mortality.

CF is caused by a defect in the gene encoding CFTR, an epithelial chloride (Cl) ion channel that is responsible for aiding in the regulation of salt and water absorption and secretion in various tissues. This function is defective in patients with CF due to a loss of cell surface expression and/or function of CFTR.

Lumacaftor (LUM; VX-809)/ivacaftor (IVA; VX-770) combination therapy (OrkambiTM) is the first medicine designed to treat the underlying molecular defect and enhance the function of CFTR in patients homozygous for *F508del*. Orkambi is approved in the US for patients 6 years and older who are homozygous for *F508del*, and in the EU, Canada, Australia, and Switzerland for patients 12 years and older who are homozygous for *F508del*. The LUM/IVA development program is designed to support the hypothesis that an oral chronic treatment restoring CFTR function can lead to improved pulmonary and extrapulmonary manifestations of CF, prevent progressive lung damage, and ultimately prolong survival.

Details about the LUM/IVA development program can be found in the Investigator's Brochure.

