### 9.1.2.2 Follow-up

The Safety Follow-up Visit is required for 1) subjects who complete their Early Termination of Treatment (ETT) Visit <10 days after the last dose of LUM/IVA (Section 9.1.2.3); and 2) subjects who interrupt LUM/IVA treatment and complete their Week 96 Visit <10 days after the last dose of LUM/IVA; it is not required for subjects who continue onto commercially-available, physician-prescribed LUM/IVA within 2 weeks ( $\pm$  4 days) of completing LUM/IVA treatment at the Week 96 or ETT Visit.

The Safety Follow-up Visit is scheduled to occur 2 weeks ( $\pm$  4 days) after the last dose of LUM/IVA. Safety Follow-up Visit assessments are listed in Table 3-1.

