### 9.1.2.3 Early Termination of Treatment

Subjects who prematurely discontinue LUM/IVA treatment will be asked to complete the ETT Visit as soon as possible after the last dose of LUM/IVA. The assessments to be completed are listed in Table 3-1. If the ETT Visit occurs 10 days or later following the last dose of LUM/IVA, then the ETT Visit will replace the Safety Follow-up Visit, (i.e., the assessments performed will be those specified for the ETT Visit), and a Safety Follow-up Visit will not be required.

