#### 13.1.1.3 Documentation of Adverse Events

All AEs will be collected from the time the ICF is signed until the following time points:

- Withdrawal of consent
- For enrolled subjects who have a Safety Follow-up Visit: through the Safety Follow-up Visit
- For enrolled subjects who do not have a Safety Follow-up Visit, the earliest of
  - o 18 days after the last dose of study drug, or
  - o the ETT Visit, if that visit is 10 days or later following the last dose of study drug (see Section 9.1.2.3)

NOTE: Only SAEs will be collected for the Observational Cohort.

All subjects will be queried, using nonleading questions, about the occurrence of AEs at each study visit. When possible, a constellation of signs and/or symptoms will be identified as 1 overall event or diagnosis. All AEs for enrolled subjects will be recorded in the CRF and source document. AEs for subjects who are screened but not subsequently enrolled in the study will be recorded only in the subject's source documents. The following data will be documented for each AE:

- Description of the event
- Classification of "serious" or "nonserious"
- Date of first occurrence and date of resolution (if applicable)
- Severity

- Causal relationship to study drug(s)
- Action taken
- Outcome
- Concomitant medication or other treatment given

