## 13.2.3 Investigator Compliance

No modifications to the protocol will be made without the approval of both the investigator and Vertex. Changes that significantly affect the safety of the subjects, the scope of the investigation, or the scientific quality of the study (i.e., efficacy assessments) will require IRB/IEC notification before implementation, except where the modification is necessary to eliminate an apparent immediate hazard to human subjects. Vertex will submit all protocol modifications to the required regulatory authorities.

When circumstances require an immediate departure from procedures set forth in the protocol, the investigator will contact Vertex to discuss the planned course of action. If possible, contact will be made before the implementation of any changes. Any departures from the protocol will be fully documented in the source documentation and in a protocol deviation log.

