**Table 13-1 Study VX16-809-116: Treatment Cohort - Treatment Period and Safety Follow-up Visit**

Event/Assessment a	Treatment Period					ETT Visit b	Safety Follow-up Visit c
	Day 1 d	Day 3 (± 1 Day)	Day 15 (± 3 Days)	Weeks 12, 24, 36, 48, 60, 72, 84 (± 7 Days)	Week 96 (± 7 Days)	As Soon as Possible After the Last Dose	2 Weeks (± 4 Days) After the Last Dose
Medications, treatments, and procedures review	Continuous from signing of ICF through Safety Follow-up Visit (if required)						
Adverse events	Continuous from signing of ICF through Safety Follow-up Visit (if required)						

AE: adverse event; BMI: body mass index; ECG: electrocardiogram; ETT: Early Termination of Treatment; ICF: informed consent form; IVA: ivacaftor; LCI: lung clearance index; LUM: lumacaftor; OE: ophthalmological examination; PE: physical examination; q12h: every 12 hours

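### The SAP's definition of a study completer has no exception for Week 96 finishers whose Safety Follow-up Visit is waived because they move to commercial LUM/IVA (minor)

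*SAP*

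**What the plan says.** SAP 10.2.1 lists the disposition rows, with the 116 Safety Set as denominator. *Completed treatment* and *Prematurely discontinued treatment* are separate from the two study-status rows. The study completer row reads "Completed study (any subject who has completed the Safety Follow-up Visit", and Protocol 12.3.2.1 defines it in the same way.

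Protocol 9.1.2.2 makes the Safety Follow-up Visit conditional. For subjects who move to commercial drug, "it is not required for subjects who continue onto commercially-available, physician-prescribed LUM/IVA within 2 weeks" (± 4 days) of finishing treatment, whether at the Week 96 Visit or the Early Termination of Treatment (ETT) Visit. The SAP repeats this waiver in Figure 7-1 footnote c and in Appendix A, Table 13-1, footnote c.

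SAP 10.2.1 has one provision on commercial drug: "Subjects prematurely discontinue treatment before Week 96 due to commercial drug available will be captured in the CRF pages", with the reason entered as free text under the *Other* category. It covers treatment stopped before Week 96 and the reason dosing ended. It does not mention a switch at Week 96 or study completion.

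**The concern.** The completer definition depends on a visit that the protocol waives for some subjects who reach the end of treatment. A Week 96 finisher who goes straight onto commercial LUM/IVA and does not attend the waived visit counts under *Completed treatment*. As the SAP is written, that child does not count under *Completed study*.

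The child then has two possible places. One is *Prematurely discontinued the study*, and so the discontinuation listing, with no true reason to report. The other is neither study-status row, so that the two rows do not add up to the 116 Safety Set. The documents do not say which, so two programmers could produce different tables from the same data. In a 96-week rollover study whose primary objective is long-term safety, readers will use study completion to judge retention. A study-completion figure below the treatment-completion figure could look like loss after Week 96 when none occurred.

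**Working it through.** **1. Can an exception be read in?** Elsewhere the documents say when the visit is conditional. The medication and adverse event rows of SAP Table 13-1 run "Continuous from signing of ICF through Safety Follow-up Visit (if required"). Protocol 13.1.1.3 sets a separate end of adverse event collection: "For enrolled subjects who do not have a Safety Follow-up Visit, the earliest of" two time points. The documents therefore plan for enrolled subjects without this visit. The completer definition has no such qualifier, and no other section supplies one.

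**2. The plan's own figure.** Protocol 12.1 and SAP 7.2 give about 56 potentially eligible subjects and 10% dropout in Study 115B. 56 × (1 − 0.10) = 50.4, which agrees with the stated 50. No completer count or rate is stated.

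**3. Effect per child.** One affected child changes study completion by 1/N, where N is the size of the 116 Safety Set.

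| N | Basis | Change per child |
|---|---|---|
| 56 | all potentially eligible subjects treated | 1/56 = 1.8 points |
| 50 | expected enrolment, all treated | 1/50 = 2.0 points |
| 40 | assumed | 1/40 = 2.5 points |

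**4. Range of the total (assumptions only).** Suppose that 50 are treated, that 5 stop early and none of these attends the Safety Follow-up Visit, and that 45 reach Week 96. Suppose also that every finisher who does not take the commercial route attends the visit. If w finishers take the route and skip the visit, the literal count is 45 − w:

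- w = 0: 45/50 = 90%
- w = 11: 34/50 = 68%
- w = 22: 23/50 = 46%
- w = 45: 0/50 = 0%

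If waived finishers are counted, the result is 45/50 = 90% in every case. The documents do not say where in this range w lies.

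**5. Could the route be open to anyone?** Protocol 5.1 states that "Orkambi is approved in the US for patients 6 years and older". With no rollover gap, the time from first Study 115B dose to Week 96 is 24 + 2 + 96 = 122 weeks = 854 days, and 854/365.25 = 2.34 years. Then 6 − 2.34 = 3.66 years. A US child aged about 3 years 8 months or more at first dose is therefore at least 6 at Week 96. This shows that the route can exist; it does not show how many would use it.

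**The case against.** The strongest reply is that this is a labelling matter in one descriptive table and may never arise.

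- The visit is waived, not barred. A child who attends it anyway is counted.
- Study status may be recorded by the site on the eCRF rather than derived from attendance. The SAP cites eCRF v2.0, which is not available here.
- The approval status in Protocol 5.1 is that of an October 2016 protocol. US children who turn 6 earlier might switch before Week 96, where the SAP already has a rule. The age calculation therefore does not identify Week 96 switchers.

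All of this stands as a limit on size and certainty. None of it supplies the missing exception.

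A reader might also infer more than the documents support:

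- *That these children will be reported as premature discontinuers.* Nothing places them there; falling in neither row is equally possible.
- *That safety follow-up is lost or a safety result distorted.* Protocol 13.1.1.3 has its own end of collection for subjects without the visit, and treatment completion and exposure are reported separately.
- *That the whole definition fails and should be rebuilt on Week 96 attendance.* Counting early stoppers who attend the Safety Follow-up Visit may be intended, since the wording covers any subject. For a late ETT Visit, Protocol 9.1.2.3 says "then the ETT Visit will replace the Safety Follow-up Visit", which can be read as letting the ETT Visit stand in for it. For other Week 96 finishers, the answer depends on what *interrupt* means in Protocol 9.1.2.2. No error is shown for any of these groups.

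**Conclusion.** The concern holds in a narrow form, and it is minor. Applied literally, SAP 10.2.1 does not count as a study completer a Week 96 finisher who moves to commercial LUM/IVA within the allowed window and does not attend the waived visit. The size is about 2 percentage points of reported study completion per such child, assuming 50 treated. The total is unknown and could be zero. The conclusion assumes that the status is derived as the SAP words it. The effect stops at the study-status rows and, depending on how the child is classified, the discontinuation listing. The analysis sets and the safety and pharmacodynamic estimates do not use this status.

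**What to change.** Change the SAP only. Keep the present definition of *Completed study* and add one clause:

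> or who has completed the Week 96 Visit and for whom the Safety Follow-up Visit was not required because the subject continued onto commercial LUM/IVA (Protocol 9.1.2.2)

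Show the number completing by each route. Leave the handling of early stoppers and the visit rules as they are.

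The cost is one clause, a revised flag and the split by route. The protocol text can stay, which avoids the process in Protocol 13.2.3 ("No modifications to the protocol will be made without the approval of both the investigator and Vertex").

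The downside is that visit and last-dose dates alone will not show who took the commercial route. The start of commercial drug must be confirmed from CRF or medication data. The SAP describes CRF capture of switching only before Week 96, and medication review is tied to the Safety Follow-up Visit where that visit is required. A few site queries may be needed. They are best raised before database lock, because SAP section 4 requires later changes to be documented in the clinical study report.
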